- Had a record of active cancer, defined as first diagnosis of cancer with V code (a special code applied to patients with confirmed diagnosis of cancer by Korean Ministry of Health and Welfare for reimbursement for 5 years or longer if recurrent/metastatic) within the past 6 months of period prior to index date; or receiving anti-cancer treatment (chemotherapy, radiation therapy, or cancer-related surgery) under cancer diagnosis with V code within the past 6 months period prior to index date

Follow-up

- **Phase I of the study:** Patients will be followed-up from the index date until the earliest of in-hospital death or end of the study period (31 Dec 2019).
- **Phase II of the study:** Patients will be followed-up from the index date until the earliest of outcome occurrence (bleeding event), treatment discontinuation, switch to another anticoagulant, in-hospital death, or end of the study period (31 Dec 2019), where patients will be considered to have discontinued treatment when new prescription is absent within the 30-day grace period after the end of the former prescription.

- **Variables**

Exposure(s)

- Anticoagulant therapy (PAC [LMWH, UFH, others], NOACs [apixaban, dabigatran, rivaroxaban, edoxaban], warfarin).

Outcome(s)

- **Phase I of the study:** sociodemographic and clinical characteristics of patients with VTE, utilization of index anticoagulant treatment, treatment patterns (including treatment interruption, switching, complete discontinuation), overall treatment duration, and clinical events preceding first treatment change
- **Phase II of the study:** Primary or secondary diagnosis with major bleeding (by site: intracranial, gastrointestinal [GI], and other sites) after the index date

Covariate(s)

- Sociodemographics (age, sex) will be assessed on the index date. Clinical characteristics including comorbidities, previous use of medications, and the number of outpatient visits will be assessed within the 6-month period prior to the index date

- **Data sources**

- South Korea's Health Insurance and Review Assessment Service (HIRA) database

- **Study size**

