5. INTRODUCTION

Venous Thromboembolism (VTE), which includes deep vein thrombosis (DVT) and pulmonary embolism (PE), is a major cause of morbidity, mortality and healthcare expenditure. Although the occurrence of VTE in the Asian population has been lower than in Western populations, Its incidence has been reported to have increased rapidly in recent years.

For pharmacologic treatment of patients with VTE without cancer, the American College of Chest Physicians (CHEST) guidelines recommend the use of Non-Vitamin K antagonist oral anticoagulants (NOACs) over Vitamin K Antagonists (VKAs), with supporting evidences suggesting that each NOAC (e.g., apixaban) is effective at preventing recurrent VTE. In more recent treatment guidelines for the management of VTE released by the American Society of Hematology (ASH), NOACs are still recommended over VKAs for the initial management of VTE. NOACs are classified as new generation of anticoagulants with approved indications of the risk reduction of stroke and embolism in nonvalvular atrial fibrillation (NVAF) as well as prophylaxis and treatment of DVT and PE.

All NOACs became available as the first-line treatment of acute VTE in Korea after reimbursement expansion in May 2015. However, despite the increasing use of NOACs among VTE patients, there are still limited real-world evidence that assess treatment patterns as well as effectiveness and safety of the different anticoagulants especially among Asian population.

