8.4. Variables

Exposure

- **Phase I of the study:** PAC (UFH [Anatomical Therapeutic Chemical [ATC] code: B01AB01], LMWH [B01AB04, B01AB05, B01AB06, B01AB12], VKA (warfarin [B01AA03]), NOACs (apixaban [B01AF02], rivaroxaban [B01AF01], edoxaban [B01AF03], dabigatran [B01AE07])
- **Phase II of the study:** Apixaban (B01AF02), Rivaroxaban (B01AF01), Edoxaban (B01AF03), Dabigatran (B01AE07), Warfarin (B01AA03)

Outcome(s)

- **Phase I of the study**

- Sociodemographic and clinical characteristics of patients with VTE who initiated anticoagulants.
- Utilization of different anticoagulants at treatment initiation. Patients will be classified based on their index anticoagulant treatment received within 30 days after being diagnosed with VTE.
- Treatment interruption from the index anticoagulant treatment, which will be defined as when a patient has a gap with no new treatment within 30 days of the estimated end of supply, but subsequently restarts the index treatment after this period.[1] The time to treatment interruption will be defined as the period from the index date to the date of treatment interruption.
- Treatment switching will be defined as a prescription of another anticoagulant therapy that is started after the treatment initiation of the index anticoagulant treatment and within 30 days after the estimated end of supply of the index anticoagulant drug (exposure to the new anticoagulant treatment must last for at least 30 days to be considered as a treatment switch). The time to treatment switch will be defined as the period from the index date to the date of treatment switch.

Exemption: As heparin can be initiated at acute stage of DVT/PE before clinical decision to use OAC, a switch from initial heparin treatment to an OAC within 2 weeks after heparin treatment initiation will not be considered a treatment switch.

- Treatment discontinuation (complete discontinuation; no reinitiation) will be defined as when a patient who ended their first continuous treatment episode with the index anticoagulant treatment without switching, and subsequently have no further prescriptions for that respective anticoagulant treatment during all available follow-up time. The time to treatment discontinuation will be defined as the period from the index date to the date of treatment discontinuation.
- Overall anticoagulant treatment duration will be defined as the time period from the index date to the earliest of treatment interruption, switch, or discontinuation.

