- If a patient has evidence of a repeat prescription within 30 days of the end of their prescription and does not experience any of the above events (treatment interruption, switch, or discontinuation), they will be assumed to be persistent on treatment.[1]
- Clinical event preceding first treatment change will be defined as occurrence of any event listed below within 30 days before treatment interruption, switch, or discontinuation. A new clinical event will be considered 'new' when it occurs for the first time within a 6-month period for acute conditions (arterial thromboembolism, ischemic stroke, transient ischemic attack, myocardial infarction, angina pectoris, acute kidney injury, and abnormal liver function) and 5-years for chronic conditions (cancer, chronic kidney disease, and liver disease). A patient may contribute to multiple events.
 - ① Major bleeding (as defined in Phase II)
 - ② Complications of VTE: post-thrombotic syndrome and chronic thromboembolic pulmonary hypertension
 - ③ Thromboembolism: PE diagnosis in patients with index event as DVT only, new diagnosis of arterial thromboembolism, ischemic stroke, transient ischemic attack, myocardial infarction, or angina pectoris
 - ④ Major surgery: orthopedic surgeries (knee arthroplasty, hip arthroplasty, and hip fracture surgery), cancer surgeries (stomach, colorectal, hepatobiliary, pancreatic, breast, ovarian, cervical, renal, bladder, prostate, lung, and esophageal cancers, and brain tumors), and benign surgeries (myomectomy, oophorectomy, and transurethral resection of the prostate)
 - ⑤ Cancer-related event (among non-active cancer patients only): new diagnosis of active cancer
 - ⑥ Kidney function change: new diagnosis of chronic kidney disease or acute kidney injury
 - ⑦ Liver function change: new diagnosis of liver disease or abnormal liver function

Clinical event preceding first treatment change	ICD-10 diagnosis code
Major bleeding	Defined in Phase II
Complications of VTE	
Post-thrombotic syndrome	I87.0
Chronic thromboembolic pulmonary hypertension	I27.2
Thromboembolism	
PE diagnosis	I26.0, I26.9
Atrial thromboembolism	I74
Ischemic stroke	I63
Transient ischemic attack	G45.9
Myocardial infarction	I21
Angina pectoris	I20
Major surgery	
Orthopedic surgeries	N0305, N0601, N0611, N0641, N0711, N2070, N0715, N2710, N0731, N0981, N0991, N1711, N3710, N1721, N3720, N1715, N4710, N1725, N4720, N2072, N2077, N2712, N2717, N3712, N3717, N3722, N3727, N4712, N4717, N4722, N4727

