10. STATISTICAL ANALYSIS

All statistical analyses will be performed using SAS Enterprise Guide 7.1 (SAS Institute Inc., Cary, NC, USA), provided by HIRA through a virtual access machine.

Phase I of the study (descriptive)

Main Analysis

- Descriptive analysis will be conducted separately in two cohorts of non-cancer VTE and cancer VTE patients according to co-presence of active cancer.
- Sociodemographic and clinical characteristics will be summarized with means (standard deviations [STD]) or median (interquartile range [IQR]) for continuous variables and with count (proportions) for categorical variables for the three treatment groups of interest: PAC only (UFH, LMWH, UFH+LMWH), warfarin-based (warfarin, PAC/warfarin) group, NOAC-based (NOAC, PAC/NOAC) group. NOAC-based (NOAC, only group, PAC/NOAC) group. Analysis of variance, and chi-square test will be conducted for continuous variables, and categorical variables, respectively.
 - In order to distinguish between PAC bridging therapy and PAC treatment, we will apply a time restriction of 2 weeks to PAC bridging therapy.
- Temporal trend in anticoagulation therapy for VTE will be presented between 1 Mar 2013 and 30 Jun 2019. Proportions of the index OACs will be estimated according to calendar year and quarter.
- The number and percentage of patients who discontinue treatment completely, experience treatment interruption and treatment switch during their follow-up will be described by the index anticoagulant treatment received. Results will be limited to the first of each of these events for each patient. For patients experiencing a treatment switch, the new treatment will be described at the time of their first switcher per individual drug.
- The duration of the index treatment by the index anticoagulant treatment received will also be summarized in terms of days using descriptive statistics (mean [STD], median [IQR]).
- The Kaplan-Meier method will be applied to derive the empirical distribution of time to each of the treatment endpoints of interest (e.g., treatment discontinuation or switch); these analyses will be performed per index anticoagulant treatment received and no comparisons will be made. Log-rank test will be conducted at the 3-, and 6 months after treatment initiation to assess statistical significance between the survival curves. Persistent rate will also be calculated at the same time point.

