Myocardial infarction
Stroke
Trauma
Previous use of medications (n, %)
Corticosteroids
NSAIDs
ACE inhibitors
Angiotensin II receptor blockers
Antiplatelets
β-blockers
Calcium-channel blockers
SSRI
Proton pump inhibitors
Diuretics
Thiazides
Vasodilators
Estrogens
Cyclooxygenase-2 inhibitors
Triazole antifungal agents
Outpatient visits (mean±std)

Table 4. Baseline characteristics among venous thromboembolism patients with active cancer by their index non-vitamin K antagonist oral anticoagulant treatment

Characteristics	Apixaban N= (%)	Dabigatran N= (%)	Edoxaban N= (%)	Rivaroxaban N= (%)	p-value
Follow-up (days; median, IQR)					
Age (years; mean±std)					
Age group (years; n, %)					
18-40					
40-65					
≥65					
Sex (n, %)					

Male

Female

Index VTE event (n, %)

DVT only

PE with or without

DVT

Health insurance type

(n, %)

National health

insurance

Medical aid

Veterans

Index year (n, %)

2013

2014

2015

2016

2017

2018

2019

CCI score (mean±std)

HAS-BLED score

(mean±std)

Comorbidities (n, %)

Antiphospholipid

syndrome

Asthma

History of cancer

COPD

Chronic kidney

disease

Chronic liver disease

Diabetes mellitus

Fracture

Heart failure

Hyperlipidemia

Hypertension

Ischemic heart

disease

Myocardial infarction

Stroke

Trauma

Previous use of

medications (n, %)

Corticosteroids

NSAIDs

ACE inhibitors

Angiotensin II

receptor blockers

Antiplatelets
β-blockers
Calcium-channel
blockers
SSRI
Proton pump
inhibitors
Diuretics
Thiazides
Vasodilators
Estrogens
Cyclooxygenase-2
inhibitors
Triazole antifungal
agents
Outpatient visits
(mean±std)

Table 5. Treatment pattern of anticoagulant therapy among venous thromboembolism patients without active cancer for the treatment groups of interest

	Warfarin-based therapy	NOAC-based therapy	PAC only
	N=	N=	N=
	(%)	(%)	(%)
Overall treatment duration (days)			
Mean, std			
Median, IQR			
3-month persistence (%)			
6-month persistence (%)			
Treatment switching (n,%)			
Mean, std			
Median, IQR			
Treatment continuation (n,%)			
Mean, std			
Median, IQR			
Treatment discontinuation (n,%)			
Mean, std			
Median, IQR			
Treatment interruption (n,%)			
Mean, std			
Median, IQR			
Death (n,%)			
Mean, std			
Median, IQR			

Note: PAC, parenteral anticoagulants; NOAC, non-vitamin K antagonist oral anticoagulant; IQR, Interquartile range; std, standard deviation

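### Overall treatment duration has no end point for patients still on treatment or dying on treatment, and its plain mean and median ignore censoring

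*SAP*

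**What the plan says.** SAP section 8.4 and Protocol section 9.3 define duration identically: "Overall anticoagulant treatment duration will be defined as the time period from the index date to the earliest of treatment interruption, switch, or discontinuation". The next item in both covers a patient who keeps refilling and "does not experience any of the above events (treatment interruption, switch, or discontinuation), they will be assumed to be persistent on treatment". It gives that patient no end date, censoring date or exclusion rule.

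In-hospital death is not among the three events that end duration, although it ends Phase I follow-up. The Protocol abstract says: "Patients will be followed-up from the index date until the earliest of in-hospital death or end of the study period (31 Dec 2019".

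SAP section 10 (Phase I, Main Analysis) says that duration by index treatment "will also be summarized in terms of days using descriptive statistics (mean [STD], median [IQR". Tables 5–6 carry this out in a row labelled "Overall treatment duration (days", side by side for warfarin-based, NOAC-based and PAC-only therapy. Tables 7–8 do the same for each NOAC. The same shells hold a row labelled "Treatment continuation (n" and a death row, each with its own mean and median. Nothing says whether those times enter the overall duration row.

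Section 10 also plans Kaplan-Meier curves for each treatment endpoint (Figures 1–3: interruption, switching and discontinuation) and persistence at 3 and 6 months.

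**The concern.** Overall duration is named in a primary objective of Phase I, and the tables set it out by drug for the reader to compare. With no rule for patients who have not had an event, a programmer has two natural choices: leave them out, which removes the longest durations, or enter time to the cut-off as if treatment had ended there. Two analysts could follow the SAP and report different numbers, and both would understate the mean.

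The understatement need not be equal across groups. Follow-up closes on one calendar date for everyone, while SAP section 5 says: "All NOACs became available as the first-line treatment of acute VTE in Korea after reimbursement expansion in May 2015". A group that enters later has less time in which long durations can be seen. Part of any warfarin–NOAC difference in the duration row could therefore reflect date of entry and not how long patients stay on the drug.

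**Working it through.** The documents state no treatment duration, so there is no planned figure to reproduce.

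**Follow-up available (calendar arithmetic to 31 Dec 2019)**
- From 1 Mar 2013, the start of the diagnosis window: 2,496 days (6.83 years).
- From 1 May 2015, the reimbursement expansion: 1,705 days (4.67 years), which is 791 days less.
- From 30 Jun 2019, the end of the diagnosis window: 184 days (0.50 year). Treatment may start up to 30 days after diagnosis, so the minimum is 154 days (30 Jul 2019).

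**Assumptions (not in the documents).** True duration T is exponential with the same mean m in both groups. Potential follow-up C is uniform on (a, b) and independent of T. Warfarin: a = 0.5, b = 6.83 years. NOAC: a = 0.5, b = 4.67 years. Death is not modelled.

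**Formulas**
- Share still on treatment: q = m/(b−a) × [exp(−a/m) − exp(−b/m)]
- Mean if ongoing patients are cut at study end: m(1 − q)
- r = m/(b−a) × [(a+m)exp(−a/m) − (b+m)exp(−b/m)]
- Mean if ongoing patients are dropped: m − r/(1 − q)

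**Worked case, m = 1 year**
- Warfarin: q = (0.6065 − 0.0011)/6.33 = 0.0956; cut mean 0.904; r = 0.1424; dropped mean 1 − 0.1424/0.9044 = 0.842.
- NOAC: q = (0.6065 − 0.0094)/4.17 = 0.1432; cut mean 0.857; r = 0.2054; dropped mean 1 − 0.2054/0.8568 = 0.760.

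| True mean (years) | Cut: warfarin / NOAC | NOAC shorter by | Dropped: warfarin / NOAC | NOAC shorter by |
|---|---|---|---|---|
| 0.25 | 0.2487 / 0.2480 | 0.3% | 0.2460 / 0.2439 | 0.9% |
| 0.5 | 0.4855 / 0.4780 | 1.5% | 0.4701 / 0.4539 | 3.4% |
| 1 | 0.904 / 0.857 | 5.3% | 0.842 / 0.760 | 9.8% |
| 2 | 1.529 / 1.346 | 12.0% | 1.315 / 1.073 | 18.5% |

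**Medians and entry mix.** These were simulated with 1,000,000 patients per group, identical Weibull durations (shape 1.0 or 0.7) and true medians of 90, 180 or 365 days.
- Uniform entry, ongoing patients cut: the medians agree between groups at 90 and 180 days. At 365 days they are 330 v 317 (shape 1.0).
- Uniform entry, ongoing patients dropped: the NOAC median is 1 to 36 days shorter.
- Warfarin entry weighted early and NOAC entry weighted late (mean potential follow-up 1,725 v 691 days): the NOAC mean is 3.4–38.3% shorter if cut and 8.5–45.9% shorter if dropped. The cut medians still agree within 1 day at 90 and 180 days, but are 362 v 289 at 365 days (shape 1.0). The dropped medians are 5 to 114 days shorter.
- Kaplan-Meier, censoring at 31 Dec 2019: both groups return the true median within about 2 days in every scenario.

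**The case against.** The best defence is that the plan already holds much of what is needed. Persistence at 3 and 6 months describes the same composite, since a persistent patient is one with no interruption, switch or discontinuation, and nearly all patients have that much potential follow-up. The continuation and death rows do give times to the patients in question. Tables 1–4 show follow-up and index year by treatment, so unequal observation time would be visible. Phase I is descriptive: Tables 5–8 have no p-value column and no test of duration is planned. If treatment typically lasts about six months or less and ongoing patients are cut at study end, the median hardly moves and the mean moves by a few per cent under uniform, exponential assumptions.

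All of this stands as a limit on the harm, but none of it corrects the duration row. Three separate single-endpoint curves do not give the time to the first of the three events. Persistence says nothing beyond 6 months. The continuation and death rows are not linked to overall duration.

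A reader might go further and infer three things that the documents do not support:
- **A gap of up to 35%.** That comes from setting NOAC users against only those patients indexed before May 2015 (1.07 v 1.65 years with a true mean of 2 years and ongoing patients dropped; 1 − 1.07/1.65 = 35%). The warfarin-based column covers all index years, and the study-size section projects about 3,900 to 4,300 new warfarin users a year from 2018 data.
- **No NOAC use before May 2015.** Section 5 dates first-line availability of all NOACs. It does not exclude earlier use, and Tables 3–4 keep 2013 and 2014 index-year rows.
- **NOAC durations are certain to look shorter, in the median as well as the mean.** This depends on an unstated handling rule, the entry mix and the true durations.

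**Conclusion.** The concern holds in a limited form. Overall duration is undefined for patients still on treatment at 31 Dec 2019 and for those who die in hospital on treatment, and the stated summary makes no allowance for censoring. If entry date and duration are independent, either natural handling biases the mean downward, and can do so more for later-entering groups. Like for like, under identical exponential durations and uniform entry, the spurious shortfall in the NOAC mean runs from under 1% (true mean 0.25 year) to about 18% (true mean 2 years, ongoing patients dropped). It grows if warfarin entry is concentrated in the early years. The true size cannot be settled from the documents. The defect merits correction because the outcome belongs to a primary Phase I objective and the remedy costs little. It does not touch Phase II, which states its own follow-up end points.

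**What to change.** 1. In SAP section 8.4 (and Protocol section 9.3), define overall duration as time from index to the first of interruption, switch or discontinuation, censored at in-hospital death or 31 Dec 2019.
2. In section 10 and Tables 5–8, replace the raw mean (STD) and median (IQR) of overall duration with the Kaplan-Meier median and quartiles, and the restricted mean to a common horizon, for example 12 months. Note beside it that minimum follow-up is about 5 to 6 months, so the latest entrants are censored before that horizon.
3. State how the continuation and death rows relate to overall duration. Showing them as the counts censored for each reason would let the reader see how much of the censoring is death, which may matter in the active-cancer tables.

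The cost is SAP wording with the matching Protocol text, and table-shell edits. No new data are needed.

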- In the NOAC-based group, all analyses will be repeated stratified by each individual NOAC class (e.g, apixaban, dabigatran, rivaroxaban, edoxaban) to

PFIZER CONFIDENTIAL

identify the difference in baseline characteristics and treatment patterns between each NOAC class.

- To identify potential reasons for treatment change, clinical events preceding the first treatment change (major bleeding, thromboembolism diagnosis, complications of VTE, major surgery, active cancer, a new diagnosis of CKD or AKI, a new diagnosis of liver disease or abnormal liver function) will be measured within 30 days prior to the first date of treatment change. Patients can contribute with multiple events.
- All analyses of treatment patterns will be presented stratified according to the index anticoagulant treatment, and not overall or per drug class.

Phase II of the study (comparative)

Propensity score analysis

- To balance and adjust for any potential differences in baseline sociodemographic and clinical characteristics between treatment groups, propensity score (PS) methods will be implemented.
 - A logistic regression model will be used to estimate the predicted probability (propensity) of initiating each NOAC compared with warfarin given baseline covariates mentioned above. By using the estimated PS, we will apply the PS based on the inverse probability of treatment weights (IPTW), where the treatment group of interest will be given a weight of 1/PS, and the comparator group will be given a weight of 1/(1-PS) [4, 5]. The most extreme 1% of PS values (IPTW with trimming) will be excluded to improve comparability between exposure groups.

Main Analysis

- Sociodemographic and clinical characteristics will be summarized with means (STD) or median (IQR) for continuous variables and with count (proportions) for categorical variables for the two treatment comparisons of: apixaban vs warfarin, rivaroxaban vs warfarin, edoxaban vs warfarin and dabigatran vs warfarin (and NOAC vs NOAC, if scientifically feasible).
 - Differences in baseline covariates between users of different OACs will be assessed using the SD where the absolute SD <0.1 will be considered as well balanced.
- The incidence rate of major bleeding overall and by site will be presented as the total number of events per 1,000 person-years, with its 95% CIs estimated using the Poisson distribution.

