- The risk of major bleeding according to the treatment of interest will be investigated in time-to-event analyses using standard Kaplan-Meier methods.

- Cox proportional hazards model will be used to compare the safety outcome between users of different OACs, weighted on the estimated PS according to the IPTW approach.
 - Proportionality assumption will be tested by use of Schoenfeld residuals.

Subgroup Analysis

- The potential heterogeneity of treatment effects in selected subgroups of patients with VTE will be examined for the major bleeding as follows:
 - Aged <65 years vs. aged \geq 65 years
 - Females vs. males
 - Setting of VTE diagnosis (inpatient vs. outpatient)
 - Type of VTE (DVT without PE [ICD-10: I80.2, I80.3] vs. PE with or without DVT [I26.0, I26.9])
 - Major orthopedic surgery-provoked VTE
 - Major orthopedic surgery-provoked VTE is defined as an event preceded by knee arthroplasty, hip arthroplasty, or hip fracture surgery (National Procedure Codes: N0305, N0601, N0611, N0641, N0711, N2070, N0715, N2710, N0731, N0981, N0991, N1711, N3710, N1721, N3720, N1715, N4710, N1725, N4720, N2072, N2077, N2712, N2717, N3712, N3717, N3722, N3727, N4712, N4717, N4722 or N4727) within 3 months period prior to index date
 - With vs. without CKD stage 3 or 4 (N18.3, N18.4)
- P-for-interaction value <0.05 will be used to denote a significant difference between the two groups.

Sensitivity Analysis

- Vary the definition of treatment interruption/discontinuation to 15 and 60 days (allowing for varying non-adherence) to assess the effect this had on study outcomes.
- Four other approaches involving PS will be applied to determine the robustness of our study findings. First, we will vary the extreme value of PS in trimming process (most extreme 5%, and 10% will be excluded). Second, we will include the estimated PS, in addition to other covariates, into our multivariable Cox proportional hazards regression model. Third, we will stratify on the estimated PS in deciles. Last, we will apply another weighting approach, standardized mortality ratio weights, with the weights given as follows: 1 for the treatment group of interest and PS/(1 – PS) for the comparator group.[4]

- Exclude patients with a history of bleeding during the 6-month pre-index-date period in Phase II comparative analysis to evaluate the robustness of findings with respect to changes in underlying risk of patients

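### The 30-day look-back for events preceding the first treatment change has no floor at the index date, so for early changes it can count events from before anticoagulation began

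*SAP*

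**What the plan says.** SAP 8.4 and Protocol 9.3 define the outcome as the "occurrence of any event listed below within 30 days before treatment interruption, switch, or discontinuation". SAP 10 repeats that events "will be measured within 30 days prior to the first date of treatment change" and gives the purpose: "To identify potential reasons for treatment change". None of these sentences limits the window to time after the index date or to days covered by supply.

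The rule for calling an event new covers a list of acute diagnoses (first in 6 months) and chronic diagnoses (first in 5 years). It does not cover surgery or VTE complications.

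Interruption is recognised when a patient "has a gap with no new treatment within 30 days of the estimated end of supply" and later restarts. Its timing is given only as follows: "The time to treatment interruption will be defined as the period from the index date to the date of treatment interruption". Discontinuation is handled the same way: "The time to treatment discontinuation will be defined as the period from the index date to the date of treatment discontinuation". Neither date is defined. A switch may start up to 30 days after the estimated end of supply.

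In the subgroup section of SAP 10, "Major orthopedic surgery-provoked VTE is defined as an event preceded by knee arthroplasty, hip arthroplasty, or hip fracture surgery" within 3 months before index. None of the SAP's 20 table shells covers the preceding-event outcome, so the shells do not settle these points.

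**The concern.** The outcome is meant to suggest why patients left their index drug. An event that happened before the drug was started cannot be a reason for leaving it, yet a literal program would count it whenever the change comes early.

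Surgery is the clearest case. The 31 orthopaedic procedure codes listed in SAP 8.4 as a preceding event are the same 31 that define surgery-provoked VTE in SAP 10. The cancer-surgery entry reuses the SAP 8.3.2 list, which helps assign patients to the active-cancer cohort from the 6 months before index. One operation could therefore be reported both as background to the VTE and as a potential reason for changing treatment.

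This outcome is the whole of the Phase I secondary objective, and treatment-pattern results are stratified by index treatment. The pre-index share depends on how early the change comes, so it can differ between strata.

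**Working it through.** The plan gives no figure to reproduce here; the check is day counting.

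**Set-up.** Index date = day 0. Index supply covers days 0 to S−1. The change is on day C. The window is the 30 days from C−30 to C−1. The 30-day window, the 30-day gap and the latest switch (30 days after end of supply) come from SAP 8.4. Values of S are illustrative, because the documents give no episode lengths.

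**Formula.** Days before index = max(0, 30 − C). The remaining days are on supply if earlier than day S and off supply otherwise.

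| Type and dating of change | C | Before index | On supply | After supply |
|---|---|---|---|---|
| Gap-based, dated at end of supply, S = 7 | 7 | 23 | 7 | 0 |
| Same, S = 14 | 14 | 16 | 14 | 0 |
| Same, S = 21 | 21 | 9 | 21 | 0 |
| Same, S ≥ 30 | S | 0 | 30 | 0 |
| Switch on day 10 of a 30-day supply | 10 | 20 | 10 | 0 |
| Gap-based, dated at end of gap, any S | S+30 | 0 | 0 | 30 |
| Switch 15 days after end of supply, S = 14 | 29 | 1 | 14 | 15 |
| Switch 15 days after end of supply, S = 90 | 105 | 0 | 15 | 15 |
| Switch 30 days after end of supply, any S | S+30 | 0 | 0 | 30 |

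Pre-index shares of the window: 23/30 = 77%, 16/30 = 53%, 9/30 = 30%.

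**Example.** Hip arthroplasty on day −10, LMWH from day 0, supply of 10 days, change dated at end of supply on day 10. The window is day −20 to day 9, with 30 − 10 = 20 days before index. The arthroplasty falls inside it and is recorded as major surgery preceding the change.

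**Which events are exposed.**
- Largely protected: major bleeding, because it takes the Phase II definition, which dates bleeding after index; PE, because it counts only for DVT-only index events and VTE codes in the prior 12 months are excluded; active cancer, because it counts only in patients without it.
- Exposed: surgery, stroke or TIA, arterial thromboembolism, MI or angina, kidney and liver diagnoses, and VTE complications. The newness rule does not close this: a first MI on day −5 is still the first in 6 months.

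**The case against.** The best reply is that Phase I follow-up starts at the index date (Protocol Abstract, Follow-up; SAP 8.2), that the preceding event is listed as a Phase I outcome, and that pre-index diagnoses are already baseline comorbidities. A post-index reading is then the natural one. This shows what was probably intended, but it does not settle the rule. Follow-up governs when a change can be observed; the event window looks back from that change, and the newness rule itself looks back 6 months or 5 years. Where the authors want a post-index limit, as for the bleeding date, they state it.

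Other points stand and limit the concern:
- A heparin-to-OAC change within 2 weeks is not a switch, which removes many very early changes.
- Anyone with an anticoagulant record in the 12 months before the VTE encounter is excluded, so the arthroplasty example needs a patient with none recorded after surgery.
- Shared procedure codes are consistent coding, not a fault in themselves. The trouble comes only from overlapping time windows.
- The shares above are shares of window days, not of events or patients.
- The SAP speaks of potential reasons under an exploratory objective.

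A reader might infer that pre-index and post-supply events both enter the same window for interruption and discontinuation, or that no dating gives a usable window. The table supports neither. For these changes the two faults are alternatives, and end-of-supply dating works fully once supply lasts 30 days.

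Nor do the documents show that post-supply events are errors. End of supply is an estimate, and an event in the gap may explain why the patient did not refill or was switched.

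**Conclusion.** The concern holds as a defect in the window definition. As written, a change before day 30 lets the look-back reach before treatment, by 30 − C days, for the exposed event types. The undefined interruption and discontinuation dates are a second, separate gap: under end-of-gap dating all 30 days fall after the estimated end of supply, whatever the supply length. Two programmers could both follow the SAP and use windows that do not overlap for the same patient.

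The size in patients cannot be stated. It would be tempting to say that the distortion is largest in the PAC-only group; that is plausible if courses are short, but the documents give no durations to support it. The day counts rest on a literal reading of the look-back and on illustrative supply lengths. The consequence is confined to an exploratory Phase I secondary outcome. It should be corrected because the rule can report what preceded or provoked the VTE as a potential reason for the treatment change.

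**What to change.** In SAP 8.4 and Protocol 9.3, state that:

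1. The window runs from the later of the day after the index date and 30 days before the change, up to the change.
2. Interruption and discontinuation are dated at the estimated end of supply.
3. A switch is dated at the first prescription of the new drug. Events between end of supply and a late switch are kept and flagged as off supply. Dropping them would leave a switch made 30 days after end of supply with no window at all.

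Align the sentence in SAP 10, and report the number of patients with a window shorter than 30 days.

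The cost is a few sentences in each document, a date condition and an off-supply flag in the program. The downside is real: very early changes get shorter windows and so less time to record an event. Show the number of shortened windows by index treatment so that readers can judge this.
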